5.3 Primary Efficacy Analysis

Change in QALYs from baseline through 18 months post-randomization will serve as the primary outcome for this trial. QALYs were chosen as the primary outcome to facilitate comparisons of the effect of depression screening with other preventive interventions as well as to facilitate cost-effectiveness analyses and policy decisions. As QALYs do not directly assess depression, this outcome measure also minimized possible patient reporting bias as a result of lack of participant blinding or masking to condition. The goal of the primary analysis is to identify whether there is difference in the change in QALYs among the three groups. QALYs describe the duration of illness per years of survival, adjusted for quality of life experienced during that survival. One year in perfect health is equivalent to 1 QALY. All patients will complete a standardized measure of quality of life using the Short Form-12 Health Survey, Version 2™ (SF-12) at baseline, and again at 6-months, 12-months, and 18-months. 1 QALYs will be estimated from the SF-12 using the Short Form 6 Duration (SF6D) which converts data from 7 items in the SF-12 assessing 6 domains (physical functioning, role limitations, social functioning, pain, mental health and vitality) to QALYs.2 Study patients who die during the study period will be assigned a utility score of 0 for assessments after the date of death. QALYs over 18 months will be calculated as the area-under-curve by interpolating linearly the scores at the four assessments (baseline, 6-month, 12-month, 18-month). There were no data obtained or available for these measures between assessments. Change in QALYs will then be obtained by subtracting the QALYs that would have occurred if there was no change in the baseline utility score from the actual QALYs that were measured across 18 months. The analysis will follow the principle of intention-to-treat and will be conducted on each imputed dataset with the point

estimate deriving from the average of 5 datasets and the pooled variance calculated using Rubin's formula.

To determine the significance of differences, we will perform a two-step gate-keeping test procedure. This will involve first performing an F-test using ANOVA, and then proceeding to do all three pairwise comparisons using two-sided t-test at 5% nominal significance *only if* the F-test has a p-value less than 0.05. With three randomization groups and three pairwise comparisons, this two-step procedure can be shown to preserve the familywise error rate in the strong sense, that is, a false positive comparison will occur at most with 5% probability under all possible scenarios._{3,4} This method is also generally more powerful than Bonferroni's adjustments.

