#### **Outcomes**

Quality-adjusted Life Year Assessment (Primary). Following the precedent set by RCTs with other depressed medical populations, we chose the Short Form Health Survey (SF-12) questionnaire to assess health related quality of life for the economic analysis. The SF-12 uses Likert scales to assess health-related quality of life aspects that are most directly relevant to depressed post-ACS patients: mobility and physical activities, ability to self-care, ability to perform usual activities, pain, and anxiety/ depression. Extensive validation, including construct validity, published normative data, and sensitivity to change have all been published for this scale. It has been used extensively the cost-effectiveness of a screening or intervention practice, and has successfully been used in depression interventions with other patients, allowing comparability with other data and settings. It is ideal for using in mail or web surveys, and takes less than 5 minutes. The NICE group in Britain recommends its use for providing cost and QALY data. We will collect deaths/dates of death from the national death index & EMR.

**Depression Symptom Assessment**. The AHA advisory suggests using the PHQ-2 (yes-no version) first, and then the full PHQ-8 for the assessment of depression symptom severity. In CODIACS QoL we will not utilize the PHQ-2, and instead ask all 8 items of the PHQ-8. The PHQ-8 has excellent psychometric properties, including sensitivity to successful change from treatment, good test-retest reliability when no treatment is offered, construct validity, reasonable correlations with health-related quality of life measures, and the ability to approximate likelihood of a major depressive

disorder. Scores on the PHQ-8 range from 0- 24 and a score of ≥10 is used for detecting likely depressive disorder, and clinically significant depression levels.

**CES-D10.** The Center for Epidemiologic Studies Depression Scale (CESD) is a screening measure (NOT a diagnostic tool) developed to identify current depressive symptomatology related to major or clinical depression in adults and adolescents. The CES-D10 is a short version of the original 20-item scale. The scores range from 0 to 30, and a score of 10 or greater is considered significant.

**Depression-free Days.** These will be calculated by using linear interpolation to estimate daily depression severity from the CES-D10 obtained at each of the four assessment points for all groups.

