# **Hypothesis 1:**

Those randomized to AHA's Depression Screen, Notify & Treat intervention group will gain significantly more quality-adjusted life years across 18 months when compared to No Depression Screen control group, and also when compared to the Depression Screen & Notify control group.

We will compare outcomes for participants randomized to each of the three groups. Change in QALYs from baseline through 18 months post-randomization will serve as the primary outcome for this trial. First, quality of life utilities will be calculated using participants' scores on the SF-12 at each visit (baseline [pre-randomization] and 6, 12,

and 18 months post-randomization). All participants who complete the SF-12 will be classified according to the SF-6D. The SF-6D describes 18,000 health states. The average profile for each randomized group will be calculated. A multiple regression formula that applies weights will be used to assign quality of life utilities for each participant. Next, QALYs will be derived by multiplying the SF-6D derived quality of life utilities by 0.5 years for each 6 month-period, assuming linearity for changes in utility within each period. Any mortality events will be assigned zero QALYs from that point to the end of follow-up. With these scores calculated, we will calculate the average QALY gained (or lost) in each randomized group compared to assuming the utility calculated at baseline remained constant across 18-months.

The goal of the primary analysis is to identify whether there is difference in QALYs among the three groups. We plan to perform a two-step gate-keeping test procedure: We will first perform an F-test using ANOVA, and then proceed to do all three pairwise comparisons using two-sided t-test at 5% nominal significance *only if* the F-test has a p-value less than 0.05. With three randomization groups and three pairwise comparisons, this two-step procedure has been shown to preserve the familywise error rate in the strong sense, that is, a false positive comparison will occur at most with 5% probability under all possible scenarios.  This method is also generally more powerful than Bonferroni's adjustments.

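### SAP 5.3 credits QALYs after death and scores all deaths in a six-month interval alike, contrary to the protocol's zero-from-death rule; the effect on the arm comparison is small

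*SAP*

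**What the plan says.** SAP 5.3 gives the death rule for the primary outcome: "Study patients who die during the study period will be assigned a utility score of 0 for assessments after the date of death". QALYs are then "calculated as the area-under-curve by interpolating linearly the scores at the four assessments", that is, at baseline and months 6, 12 and 18. The date of death is not a point on that curve. The SAP adds: "There were no data obtained or available for these measures between assessments".

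The protocol (Statistical Methods, Hypothesis 1) gives a different rule: "Any mortality events will be assigned zero QALYs from that point to the end of follow-up". It derives QALYs by "multiplying the SF-6D derived quality of life utilities by 0.5 years for each 6 month-period", "assuming linearity for changes in utility within each period". It does not describe the utility path between the last assessment and death.

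The protocol's Outcomes section says: "We will collect deaths/dates of death from the national death index & EMR".

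**The concern.** Under the SAP, the date of death matters only for deciding which interval the death falls in. Someone who dies shortly after a visit keeps earning QALYs, on a declining line, for almost six months after death. Someone who dies just before the next visit receives exactly the same amount. The protocol allows no credit after death.

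Two programmers working from the two documents would therefore compute different primary-endpoint values for nearly every decedent. The same utilities feed the incremental cost-effectiveness ratios under Hypothesis 2. What is at stake is agreement between the governing documents and a correct treatment of time after death. The possible effect on the group comparison has to be sized separately.

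**Working it through.** **Inputs from the documents.** Assessments every 0.5 years; the two death rules above; planning SD 0.17, target difference 0.031, 475 per group for 80% power at two-sided 5%, and 500 per group after 5% loss (SAP 5.4).

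**Assumptions, because the documents give no figure.** Last utility before death u = 0.7 (range 0.6 to 0.8); 15 deaths per 500 (range 5 to 50, or 1% to 10%); death times uniform within intervals. Let f be the fraction of the six-month interval lived.

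**1. The plan's own figures.** The plan gives no QALY figure for a decedent. Its design figures reproduce: the effect size is 0.031/0.17 = 0.182, 475 per group gives 80.2% power, and 475/0.95 = 500. They do not depend on the death rule. They give the yardstick for the comparison: SE = 0.17 × √(2/500) = 0.0108.

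**2. SAP credit in the interval of death.** The curve is a triangle of height u and base 0.5, so the credit is 0.25u whatever f is.

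**3. The part of that credit that falls after death.** The remaining triangle has height u(1-f) and base 0.5(1-f), so its area is 0.25u(1-f)². It is positive for every death before the next visit.

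**4. Protocol rule, zero from death.** The credit depends on the path before death:
- flat at u until death: 0.5fu
- linear fall to 0 at death: 0.25fu

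**5. SAP minus protocol, per decedent, at u = 0.7.**
- Flat: 0.25u - 0.5fu = 0.175 - 0.35f. This runs from +0.175 to -0.175 and is zero only at f = 0.5.
- Linear: 0.25u(1-f) = 0.175(1-f). This runs from +0.175 to 0 and is zero only at f = 1.

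For u from 0.6 to 0.8, the 0.175 becomes 0.15 to 0.20. The change score subtracts the same constant-baseline QALYs under either rule, so these differences pass unchanged into the primary outcome.

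**6. Example**, utility 0.7 at baseline and month 6 (QALYs to month 18):

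| Death at | SAP | Protocol, flat | Protocol, linear | SAP credit after death |
|---|---|---|---|---|
| month 7 (f = 1/6) | 0.525 | 0.408 | 0.379 | 0.1215 |
| month 11 (f = 5/6) | 0.525 | 0.642 | 0.496 | 0.0049 |

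**7. Effect on the arm comparison.**
- Flat path: the per-death difference averages zero, with SD 0.175/√3 = 0.101. Noise in the difference between two arms is 0.101 × √30/500 = 0.0011. With 5 to 50 deaths per arm it is 0.101 × √10/500 = 0.0006 to 0.101 × √100/500 = 0.0020. Adding 0.0011 in quadrature to 0.0108 raises the SE by about 0.5%, and power at 500 per arm moves from about 82.2% to 81.8%.
- Linear path: the SAP is higher by 0.175/2 = 0.0875 per death on average. Each arm mean rises by 0.0875 × 15/500 = 0.0026, which cancels if mortality is equal. One percentage point of differential mortality leaves 0.0875 × 0.01 = 0.0009, against 0.031.

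**8. Arm-specific timing.** Under the flat path, suppose all deaths in one arm fall in the first half of their intervals and those in the other arm are uniform. The mean difference is then 0.0875 per death, and the bias is 0.0875 × 15/500 = 0.0026, about a quarter of one SE.

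**The case against.** The strongest reply is that the protocol does not contain a complete rule to measure the SAP against. It fixes the value after death but not the path before it, and its linearity assumption does not settle the matter. No utility is observed between visits, so the true credit in the interval of death is unknown under any rule. This stands. A reader might infer that the protocol requires the last utility to be carried forward, and that the SAP is wrong by up to 0.175 in either direction. The text does not support that: the two-sided error belongs to the flat path only. Under the linear path, the SAP is nearly right for a death just before the next visit. What survives is the credit after death, which contradicts the protocol whichever path is chosen.

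A second reply is that dates of death may be imprecise or late. SAP 7.2 names surrogates and the medical record, while the protocol also names the death index and allows that search within five years after the study ends. The SAP rule needs only the interval of death, so it is less exposed to error in the date. This is a real cost of changing the rule. It does not justify leaving the documents in conflict.

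A third reply is that the absence of data between assessments explains the SAP rule. That statement concerns the quality-of-life measures. Utility after death needs no questionnaire.

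**Conclusion.** The conflict is certain and lies in the definition of the primary endpoint. The SAP credits 0.25u(1-f)² QALY after death and scores all deaths in an interval alike; the protocol stops credit at death. At u = 0.7, the difference per decedent ranges from +0.175 to -0.175 (flat path) or from 0 to +0.175 (linear path).

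A reader might go further and infer that the treatment comparison is biased. The documents do not support that. At 15 deaths per 500, the noise SD of 0.0011 is about a tenth of the 0.0108 standard error. The 0.0026 bias needs a pattern of death timing specific to one arm, for which neither document gives a mechanism. These sizes rest on assumed utility, mortality and death times. The case for change is that the rules should agree and the repair is nearly free, not that the result is at risk.

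**What to change.** In SAP 5.3, replace the death rule with one that adds a point on the curve at the date of death, sets utility to 0 from that date to month 18, and names one path from the last assessment to death. For example: the utility at the last assessment before death is carried to the date of death and is 0 from then on; a sensitivity analysis lets utility fall linearly from that assessment to 0 at the date of death. State the same rule under Hypothesis 1 in the protocol. Carrying the last value forward is a choice to be declared, not something the protocol already says. Also state which source supplies the date of death and what is done when only the interval is known.

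The cost is a few sentences and a few lines of code, because collection of dates of death is already planned. The downside is that a path before death must be assumed and that the rule relies on accurate dates.

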who are randomized to the AHA Depression Screen, Notify & Treat arm will also complete a PHQ-8 assessment, and those with clinically significant scores (≥ 10) will be offered the option of receiving treatment for their depressive symptoms. Participants will be presented with the option of receiving medication therapy (sertraline or bupropion), Cognitive Behavioral Therapy (delivered via phone), a combination of both therapies or neither therapy. Depending on their treatment choice, they will be scheduled for their initial treatment visit, ideally within two weeks of randomization. Their PCP and/or cardiologists will also be notified if they have clinically significant scores (≥ 10) on the PHQ-8 assessment. Those randomized to No Depression Screen group will not receive the depression screen PHQ-8 at baseline.

All participants, regardless of randomization assignment, will complete the CES-D10, SF-12 health-related quality of life measure, symptoms checklist and lost productivity at enrollment and after 6-, 12-, and 18-months of study participation. All participants will also complete the PHQ-8 assessment at 18-months, with referral to treatment for those with scores ≥ 10. Participants will be contacted by telephone, or have an in-person visit scheduled, as they prefer. These administration methods have been compared in past studies and found to be equivalent. These follow-up contacts will be brief, and scheduled at the participant's convenience wherever possible.

All participants will report their health service utilization at 6-, 12- and 18-months. Additionally, all will have EMR searches of health care utilization extracted for the 18-month duration of the trial.

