#### **Implementation**

All eligible participants who give consent will be randomized by the unblinded coordinator after completion of all baseline assessments. The randomization tool is only available to designated unblinded coordinators (UC) at each site. The UC will enter the required information in the tracking system, after which the participant's group assignment will be immediately available.

If the participant is randomized to the No Depression Screen arm, the UC will inform the participant that no further assessments are required.

If the participant is randomized to the Depression Screen and Notify arm, the UC will administer the PHQ-8. If the PHQ score is ≥ 10, the UC will notify the participant's primary care provider and/or cardiologist either through the tracking system, by email, or mail in accordance with their IRB requirements.

If the participant is randomized to the AHA Depression Screen, Notify, and Treat arm, the UC will administer the PHQ-8. IF the PHQ score is ≥ 10, the UC will inform the patient of the available treatment options. Depending on the participant's choice of treatment, the UC will facilitate the initial contact with the relevant treatment specialist(s), ideally within two weeks of randomization and will work closely with the treatment specialist(s) to monitor the participant's treatment progress. The participant's PCP and/or cardiologist will also be notified of the positive depression screen.

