#### **Statistical Methods**

All analyses will use the principle of intention-to-treat. Baseline characteristics will be examined as means (standard deviation) or percentages by randomization assignment to confirm a balanced allocation. As randomization will be performed stratified by study site, we will also assess baseline characteristics further stratified by study site. Also, participant characteristics will be compared across study site

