In a secondary analysis, we will use a mixed model with a random intercept to assess the change in quality of life utilities over time comparing individuals in the AHA Screen, Notify & Treat group vs. the other two randomization groups. This model will incorporate main effects of time (i.e., baseline, and 6-, 12-, and 18-months post-randomization), treatment group, and the time by treatment group interaction. Using this model, we will be able to calculate the mean utility at each follow-up time period for the 3 groups and determine whether the response profile differs by time across groups.

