#### **Hypothesis 2:**

Those randomized to AHA's Depression Screen, Notify & Treat intervention group will have a favorable incremental cost-effectiveness ratio when compared to No Depression Screen control group and also when compared to the Depression Screen & Notify control group.

For this hypothesis, we will judge the cost effectiveness of AHA Screen, Notify & Treat group compared to the Screen & Notify group, then we will compare the Screen & Notify group to the No Screen group on the basis of incremental cost-effectiveness ratios. The base case analysis will adopt a societal perspective with respect to costs and health benefits. Costs will include all healthcare costs and lost productivity cost related to use of website/staff time for depression screening, and the cost of all possible depression care used (antidepressant cost and therapy cost, including the cost for telephone/webcam use). Costs will be denominated in 2012 dollars and discounted at an annual rate of 3% as per the Panel on Cost-Effectiveness in Health and Medicine. For health benefits, we will convert SF-12 scores to QALYs, using the four (prerandomization, 6, 12, & 18 month) measured values. Incremental cost-effectiveness analyses for comparison of treatment groups will be calculated sequentially using the ratio of the difference in average cost per participant divided by the difference in average QALY gained.

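### The primary ANOVA on change in QALYs removes baseline utility only with a fixed weight; adding baseline SF-6D utility as a covariate would cost almost nothing and gain between near nil and substantial precision

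*SAP*

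**What the plan says.** SAP 5.3 forms QALYs as the area under the SF-6D utility curve through baseline, 6, 12 and 18 months, with utility 0 after death. It then takes off a flat projection of the baseline value: "Change in QALYs will then be obtained by subtracting the QALYs that would have occurred if there was no change in the baseline utility". The test is described as "first performing an F-test using ANOVA, and then proceeding to do all three pairwise comparisons using two-sided t-test at 5% nominal significance", the pairwise step being conditional on the F-test. Protocol Hypothesis 1 gives the same procedure ("We will first perform an F-test using ANOVA"). Neither document names a covariate for the primary test; in the SAP, covariates appear only in the imputation step (5.6).

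The covariate exists and precedes allocation. The protocol's Interventions section says "All participants, regardless of randomization assignment, will complete the CES-D10, SF-12 health-related quality of life measure", with enrollment among the listed times, and its Implementation section says participants "will be randomized by the unblinded coordinator after completion of all baseline assessments".

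The other model of utility is secondary (protocol Hypothesis 1): "we will use a mixed model with a random intercept to assess the change in quality of life utilities over time". It treats baseline as one of the outcome times.

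**The concern.** A change score fixes the baseline coefficient instead of estimating it. Where the fixed value is not the best one, the endpoint stays correlated with baseline utility and the ANOVA counts that explainable variation as noise. Confidence intervals are then wider than the same data allow, and part of any chance baseline imbalance stays in the estimate.

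The secondary mixed model does not fill the gap. Its group effect at baseline is unconstrained, so with complete data its change contrasts equal the unadjusted ones.

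Precision matters here because the planned difference is small (0.031 QALY, since only 20% of the Screen, Notify & Treat arm is expected to be treated). In addition, Hypothesis 1 claims superiority over both control arms, while the 80% power in SAP 5.4 is for a single pairwise comparison.

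**Working it through.** **Inputs from the documents.** Endpoint construction: SAP 5.3. Difference 0.031, SD 0.17, 475 per group, two-sided 5%: SAP 5.4. **Assumptions** (not in the documents): between-visit correlation ρ, ratio k of follow-up SD to baseline SD, death rate, mean utility 0.75 and utility SD 0.12-0.17.

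**1. The plan's own figure.** n = 2(1.96 + 0.8416)² × (0.17/0.031)² ≈ 472.1, so 473 per group (stated: 475). Power at 475 is 80.2%. The F-test gives 83.5% (stated: 84%). The design reproduces.

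**2. The endpoint as a contrast.** QALYs = 0.25u0 + 0.5u6 + 0.5u12 + 0.25u18. Subtracting 1.5u0 gives −1.25u0 + 0.5u6 + 0.5u12 + 0.25u18.

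**3. What remains related to baseline.** Under a common ρ, the slope of the endpoint on u0 is −1.25(1 − kρ). It is zero only when kρ = 1: ρ = 1 at k = 1, 0.91 at k = 1.1, 0.83 at k = 1.2.

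**4. Share of variance ANCOVA removes.** With k = 1, in units of the utility variance:
- Var(change) = 2.125(1 − ρ)
- Var(residual given u0) = (1 − ρ)(0.5625 + 1.5625ρ)
- Ratio = (0.5625 + 1.5625ρ)/2.125. At ρ = 0.7 this is 1.65625/2.125 = 0.779, so 22% is removed.

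The same calculation from the 4×4 covariance matrix for other structures gives:

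| Share removed (%) | ρ 0.5 | 0.6 | 0.7 | 0.8 | 0.9 |
|---|---|---|---|---|---|
| Common ρ, k = 1 | 37 | 29 | 22 | 15 | 7 |
| Common ρ, k = 1.1 | 28 | 20 | 12 | 5 | 0.1 |
| Common ρ, k = 1.2 | 20 | 12 | 5 | 0.5 | 3 |
| AR(1), k = 1 | 46 | 38 | 30 | 21 | 11 |
| AR(1), k = 1.2 | 33 | 24 | 15 | 6 | 0 |

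Simulated trials gave variance ratios of 0.63, 0.78 and 0.92 at common ρ 0.5, 0.7 and 0.9 with k = 1 (closed form 0.63, 0.78, 0.93).

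**5. Deaths scored 0.** These raise follow-up variance and shrink the gain. With death times uniform over 18 months, the shares at ρ 0.5/0.7/0.9 are:
- 1% deaths: 29-33/16-19/3-5%
- 2% deaths: 25-30/12-16/2-4%
- 5% deaths: 17-24/8-12/2-3%

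**6. Interval width.** The interval narrows by 1 − √(1 − share). At ρ = 0.7 that is 12% with equal SDs, 6-8% with 2% deaths and 4-6% with 5% deaths. Under a common ρ from 0.5 to 0.9 the range is about 0-20%.

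**7. Pairwise power at 475, if 0.17 is the SD of the change.** SD becomes 0.17√(1 − share). From 80%, power rises at ρ 0.5/0.6/0.7/0.8/0.9 to:
- k = 1: 94/92/89/86/83%
- k = 1.2: 88/85/82/80/81%
- ρ = 0.7 with deaths: 85-86.5% (2%) or 83-85% (5%)

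If 0.17 is instead the SD of 18-month QALYs, power with equal SDs and a common ρ is already 90% at ρ 0.5 (98% with ANCOVA) and above 99% from 0.7. Under AR(1) it rises from 72 to 93%, 83 to 96% and 93 to 98% at ρ 0.5/0.6/0.7.

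**8. Both comparisons through the gate.** Simulation used 2,000 trials per scenario, endpoint SD 0.17, and baseline plus four sites in the ANCOVA. At ρ = 0.7, ANOVA to ANCOVA power is 69 to 81% (equal SDs), 68 to 77% (2% deaths) and 69.5 to 75% (5% deaths). At ρ = 0.8, k = 1.2 it stays at 66%. The Monte Carlo SE is about √(0.68 × 0.32/2,000) = 1 point, so the spread in the ANOVA column among the normal scenarios is noise; a 40,000-trial run with normal data puts that value at 68.3%. The false-positive rate of the gated ANCOVA under the global null was 5.3% (2% deaths) and 4.5% (5% deaths), SE 0.3%.

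**9. Chance imbalance.** One SE of the baseline difference is SD × √(2/475), or 0.008-0.011 for SD 0.12-0.17. Multiplied by 1.25(1 − ρ), it separates the raw and adjusted estimates by 0.005-0.007, 0.003-0.004 or 0.001 at ρ 0.5/0.7/0.9 with equal SDs. That is 16-22%, 9-13% or 3-4% of 0.031.

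**10. Imputed baselines.** SAP 5.6 imputes missing baselines by random draw. With 1-5% of baselines replaced and equal SDs, the share removed is 37-38/22-23/8-9% at ρ 0.5/0.7/0.9, so the gain is not diluted.

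**The case against.** The plan already adjusts for baseline. With equal SDs, the change score achieves 49% of ANCOVA's variance reduction over raw QALYs at ρ 0.5, but 89%, 96% and 99% at 0.7, 0.8 and 0.9. The design reaches 80% power without a covariate, and no document fixes the size of the benefit. The largest gains need low correlation, equal SDs and no deaths, which is optimistic after ACS. The power argument also depends on reading 0.17 as the SD of the change; SAP 5.4 states it only for QALYs. All of this stands, and it is why the result is a range and the planned test is not called wrong.

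A second objection is technical. One slope is fitted across three arms, but the assumed benefit sits only in depressed patients, who may start with lower utility. The treated arm's slope could then differ. In corner cases (for example ρ 0.9, k = 1.1) the variance of the Screen & Notify versus No Screen contrast can rise by a few percent, at most 3-4%. That is not one of the two contrasts in Hypothesis 1, both of which still improve. The claim of being at least as precise needs this qualifier, but the conclusion does not change.

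Third, it may be too late. Recruitment is complete, the SAP is dated 1/1/2019, and the documents attest blinding only for October 2017. This limits the remedy but not the finding.

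**Conclusion.** The point holds as a recommendation on precision, not as an error. Baseline utility enters the primary test only through the fixed −1.25 weight, and a covariate measured before randomization in every arm is left unused. ANCOVA on change and ANCOVA on 18-month QALYs give the same group contrast, so the estimand is unchanged. In large samples with a common slope, ANCOVA is at least as precise as the planned test.

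The gain runs from essentially nil (k = 1.2 at ρ about 0.8, or k = 1.1 at ρ 0.9) to 37% of the variance under a common ρ of 0.5 with equal SDs, or 46% under AR(1). A middle case, ρ 0.7 with 2% deaths, gives 12-16% of variance and intervals 6-8% narrower. Every one of these figures rests on assumed correlations, SD ratios and death rates. Confidence that the gain is material is therefore medium.

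**What to change.** **If the data are still blinded**, by dated amendment to SAP 5.3 and protocol Hypothesis 1:
- Make the primary model an ANCOVA of change in QALYs on randomized group and baseline SF-6D utility. Include site as a factor, given the protocol's Statistical Methods: "As randomization will be performed stratified by study site". The Sequence generation text in both documents gives only block sizes, so confirm the stratification first.
- Keep the gate: the 2-df F-test for group at 5%, then the three adjusted pairwise contrasts at 5%.
- Fit the model in each of the 5 imputed datasets and pool by Rubin's rules, using the multi-parameter version for the F-test.
- Keep the unadjusted ANOVA as supportive. A group-by-baseline term can serve as a check on the common slope.
- Protocol Hypothesis 2 defines the cost-effectiveness ratio as a cost difference "divided by the difference in average QALY gained". Use the same adjusted QALY difference there, or state that the two differ.

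**If the data were already unblinded**, leave the primary test unchanged and report the ANCOVA as a sensitivity analysis.

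**Cost.** No new data or patients. Under the protocol's Protocol Amendments section, the change needs agreement of the overall PI, site PIs and co-investigators, and DSMB and IRB approval before implementation. Blinding status on the amendment date must be documented. The expected variance cost with N = 1,425 is 1/1,420 ≈ 0.07% for baseline alone and about 4/1,417 ≈ 0.3% with site. Raw and adjusted QALY differences will not coincide, which is why the cost-effectiveness wording needs attention.
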